7.1 Women of Childbearing Potential (WOCBP)

Pregnant or nursing (lactating) women, where pregnancy is defined as the state of a female after conception and until the termination of gestation, confirmed by a positive serum human chorionic gonadotrophin laboratory test (>5 miU/mL) will be excluded from participation in this study.

Women of child-bearing potential, defined as all women physiologically capable of becoming pregnant, including women whose career, lifestyle, or sexual orientation precludes intercourse with a male partner and women whose partners have been sterilized by vasectomy or other means must agree to use two birth control methods throughout their participation in the study. The two methods can be a double barrier method or a barrier method plus a hormonal method.

Subjects will be counseled by the study team regarding adequate forms of contraception.

- Adequate barrier methods of contraception include: diaphragm, condom (by the partner), intrauterine device (copper or hormonal), sponge or spermicide. Hormonal contraceptives include any marketed contraceptive agent that includes an estrogen and/or a progestational agent.
- Reliable contraception should be maintained throughout the study.

Women are considered post-menopausal and not of child bearing potential if they have had 12 months of natural (spontaneous) amenorrhea with an appropriate clinical profile (e.g. age appropriate, history of vasomotor symptoms) or six months of spontaneous amenorrhea with serum FSH levels > 40 mIU/mL and estradiol < 20 pg/mL] or have had surgical bilateral oophorectomy (with or without hysterectomy) at least six weeks prior to study enrollment. In the case of oophorectomy alone, only when the reproductive status of the woman has been confirmed by follow up hormone level assessment is she considered not of child bearing potential.

8. ANTICIPATED BENEFITS

Given that over 50% of patients will have a recurrent episode of pouchitis after an initial episode. Fecal microbiota transplant has the potential for preventing further episodes and obviate the need for repeated course of antibiotics if it proves to be effective.

9. DATA ANALYSIS

Patients will be identified by physicians on this protocol in The Emory Clinic or Emory

FMT in UC-associated Pouchitis

Version 3.0, date finalized 06/26/2017

University Hospital. Patients will be consented using an IRB approved informed consent and undergo the procedure on their follow up visit.

Since this is a pilot study, no formal power calculation is provided. Descriptive statistics and ANOVA will be used to detect differences between groups. One-sample t-test or Wilcoxon's signed rank-tests will be used to see if there were any significant changes in PDAI and QOL scores before and after transplant. A Simon's two stage design will be used to decide whether to enroll more patients in the future.

Data relating to laboratory results will be obtained through the EMR computerized patient information systems EML microbiological reports. A dataset will be created in a secure file, with access given only to authorized study staff.

A list of possible cases that have been reviewed for inclusion will be secured by study staff. This list will contain subject name, birth date, medical record number, and the number of the corresponding data abstraction sheet. Such a list will be maintained so as not to duplicate the abstraction of a single subject. Once the data from all included subjects is entered into a database, the list of identifiable patient information will be destroyed.

Data analysis will be performed with Microsoft Excel, SAS Institute software, and SPSS software.

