3. STUDY DESIGN

The primary investigative design will be a single arm study to determine if FMT has the potential to be used in the treatment of chronic pouchitis.

3.1 *Study Objectives:*

Primary Objective: To determine the safety and tolerability of fecal microbiota transplant (FMT) in treatment of chronic pouchitis

Secondary Objective: To study the microbial environment of IPAA/UC associated pouches in patients presenting with symptoms of pouchitis with and without endoscopy-visualized pouchitis and to assess the impact of the therapy on the patient's perceived quality of life

3.2 *Study design Type/Phase:* This is a two center, Phase 1 open label study designed to determine the safety, tolerability and use of fecal transplant in patients with pouchitis and to study the differences in microbiome in patients before and after treatment with FMT.

3.3 *Sites Centers of Research:* This study will be conducted in the Emory Clinic- Adult Digestive Disease Clinic and Colorectal Surgery Clinic, the Emory Center Endoscopy Center, and St. Joseph's Hospital (SJH) in Atlanta, GA.

3.4 *Measures to minimize/avoid bias:* Eligible subjects will be given options of other treatments if they choose not to participate.

3.5 *Study duration:* The total duration of the study for each patient will be twelve weeks.

3.6 *Study Procedures*

The following protocol essentially requires two sets of study procedures. One set of study procedures outlines testing requirements for the donor of allogenic human feces (see **Table 1.** Donor Related Study Activities). The other set outlines activities and expectations of the research participant who will receive the donated stool specimen (see **Table 2.** Research Participant Study Activities). The donor set of activities will be managed by [name], a sub-investigator and Associate Professor of Medicine within the Division of Infectious Diseases. In the past, [name] has overseen the donor recruitment and screening within previous FMT trials via ordering the appropriate antibody screens, fecal sample preparation (e.g. use of saline, etc.) and any other necessary tests to ensure that the fecal specimen is non-infectious and safe for insertion into research participants. [name] still oversees this process and prepares the allogenic human fecal FMT in UC-associated Pouchitis

Version 3.0, date finalized 06/26/2017

donation in her lab on site. However, she will not be able to provide these activities listed in **Table 1** for effort.

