3.7 Inclusion and Exclusion criteria

The following lists outline key criteria used by the principal investigator, sub-investigators, and study team to determine who can and cannot be in this study.

Inclusion Criteria

1. Males and females between the ages of 18 and 80 (inclusive) with ulcerative colitis-associated IPAA with and without pouchitis
2. Eligible patients will be identified through the Emory Clinic (TEC), St. Joseph's Hospital (SJH), and Emory University Hospital (EUH)
3. Signed informed consent

Exclusion Criteria

1. Age <18 years or >80 years of age
2. Exposure to immunosuppressive therapy within the 4 weeks prior to enrollment or their expected use within 1 month of FMT
3. Concomitant *Clostridium difficile* infection
4. Suspected Crohn's disease
5. Documented active infection of any kind
6. Patients on anti-coagulant therapy, with platelet count less than 50,000, significant anemia with hemoglobin < 7, or those with other conditions that place them at increased risk of bleeding
7. Pregnant or breastfeeding women (pregnancy will be verified using urine pregnancy kits)
8. Need for imminent surgery
9. Absolute neutrophil count (ANC) < 1000 or history of opportunistic infection
10. Administration of any investigational drug within one month before FMT

Demographic data, including prior history of pouchitis with sub-classification into chronic antibiotic resistant (refractory) pouchitis, chronic antibiotic use as well as previous treatments will be recorded. Measures of waist and hip circumference and waist to hip ratio will be calculated and recorded. Stool samples, urine, and serum samples will be collected. Patients will be screened at entry for enteric pathogens (*C. difficile*, routine bacterial stool culture, ova and parasites) and positive results will exclude entry to the study.

Fecal samples from subjects will be analyzed for microbiome genetics, and metabolomic profiles before and four weeks after therapy. Scored symptoms according to the modified pouch disease activity index (mPDAI) (**Appendix 1**) as proposed by Shen et al. will also be recorded.

FMT in UC-associated Pouchitis
Version 3.0, date finalized 06/26/2017

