documented before pouch endoscopy. Investigation with biopsy incorporating both endoscopic and histologic criteria will be pursued. As per Shen's protocol when developing the modified PDAI (mPDAI), biopsies will be taken from the posterior wall of the pouch if the pouch has abnormal endoscopic appearance and from areas of maximal inflammation (Shen 2003). In addition to the two to four biopsies that are taken for the pathologist, additional biopsies will be taken to study the epithelial microbiome.

No more than 6 total biopsies will be taken. A single gastrointestinal pathologist, blinded to the clinical presentations and endoscopic findings, will assess the pouch biopsies for grade of inflammation. On the basis of the criteria proposed by Sanborn et al patients with a total PDAI of seven or more will be classified as having pouchitis. Symptomatic patients without endoscopic and histologic evidence of pouchitis and a PDAI less than seven points will be defined as not having pouchitis. All patients undergoing pouchoscopy will receive a universal donor fecal transplant deposited in the most proximal limit of the afferent limb after the mucosal biopsies are obtained. There will be 2 categories of patients. Patients with pouchitis symptoms with endoscopic and histologic evidence of pouchitis, and patients with pouchitis symptoms without endoscopic features, but with histologic evidence of pouchitis.

We will assess patient perceived improvement in symptoms and quality of life by asking participants to complete two surveys--Short Quality of Life Questionnaire for Inflammatory Bowel Disease and the Cleveland Global Quality of Life. Participants will be asked to complete these surveys at enrollment and again at 4 weeks and 12 weeks post-FMT procedure (**Appendix 4**).

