6. REQUIRED NUMBER OF PARTICIPANTS

A total of 11 patients with IPAA/UC related pouchitis will be enrolled over 12 months as part of this pilot study.

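### Section 9 plans ANOVA between groups with no baseline adjustment; used on the clinical score by baseline PDAI class, it would mistake a built-in starting difference for a group difference

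*Combined protocol and SAP*

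**What the plan says.** - **Analysis.** Section 9 gives one sentence on between-group analysis: "Descriptive statistics and ANOVA will be used to detect differences between groups". It does not say which groups, which outcome, which visit or which covariate. The next sentence gives PDAI and QOL scores a one-sample t-test or signed-rank test before and after transplant. Section 9 also says "Since this is a pilot study, no formal power calculation is provided". No alpha is stated anywhere.
- **Design and size.** Section 3: "The primary investigative design will be a single arm study". Section 6: "A total of 11 patients with IPAA/UC related pouchitis will be enrolled over 12 months as part of this pilot study". The groups must therefore be subgroups of patients.
- **Possible groups.** Section 3.7 says "There will be 2 categories of patients": symptoms with endoscopic and histologic evidence, and symptoms with histologic evidence but no endoscopic features. The secondary objective in section 3.1 has a similar split, "with and without endoscopy-visualized pouchitis", for the microbial environment. Section 3.7 also says "patients with a total PDAI of seven or more will be classified as having pouchitis", and its inclusion criteria admit patients with and without pouchitis. Antibiotic history is recorded as "prior history of pouchitis with sub-classification into chronic antibiotic resistant (refractory) pouchitis, chronic antibiotic use".
- **Measurement.** Appendix 1 scores clinical, endoscopic and histologic components. Table 2 schedules the full index at enrollment, but only the clinical part at 2 weeks, 4 weeks and 3 months.

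**The concern.** A patient reaches a total of 7 partly through clinical points. Splitting on the total therefore also splits, on average, on the baseline clinical score. If that same score is the outcome, plain ANOVA can go wrong in two ways. On the follow-up score, it carries the starting difference forward. On change from baseline, it picks up regression to the mean: patients selected for a high score tend to fall further whatever the treatment does.

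Either result could be reported as FMT working differently by disease activity when it acts identically in everyone. Endoscopic features present versus absent carries a weaker form of the same problem, and only if the PDAI components are correlated. At stake is how the pilot's subgroup findings are read.

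**Working it through.** The plan attaches no alpha, power or effect size to the 11 patients, so there is no planned figure to reproduce. The check is of the false-positive rate.

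**1. Overlap of grouping and outcome (Appendix 1).** Clinical maximum: 2 + 1 + 2 + 1 = 6. Endoscopic maximum: 6. Histologic maximum: 3 + 3 = 6. Total: 18, so the clinical share is 6/18, or one third.

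**2. Expected size of the artefact.** Let D be the baseline clinical difference between the groups and r the correlation of a patient's clinical score before and after FMT. With equal spread and the same FMT effect in everyone, the expected difference is about r × D on the follow-up score, and about (1 − r) × D extra fall on change. Simulation (second setting below) gives D of about 1.2 to 1.6 points. For r from 0.3 to 0.7, the spurious extra fall is then between (1 − 0.7) × 1.2 = 0.36 and (1 − 0.3) × 1.6 = 1.12 points.

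**3. Simulated false-positive rates.** 11 patients; components rounded and kept within 0 to 6; identical FMT effect; groups by total of at least 7 versus below 7; two-sided 5% test. The alpha, means, SDs and correlations are assumptions, because the documents give none.

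First setting: means 3, 1.5, 2.5 and SDs 1.4, 1.6, 1.4 (clinical, endoscopic, histologic); FMT shift of −1 point; 3,000 runs per row.

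| Component correlation | Retest correlation | Spurious extra fall (points) | ANOVA on change | ANCOVA |
|---|---|---|---|---|
| 0 | 0.3 | 0.98 | 13.6% | 5.7% |
| 0 | 0.5 | 0.74 | 11.1% | 5.2% |
| 0 | 0.7 | 0.48 | 8.8% | 4.8% |
| 0.3 | 0.3 | 1.20 | 18.9% | 5.3% |
| 0.3 | 0.5 | 0.92 | 16.2% | 5.0% |
| 0.3 | 0.7 | 0.60 | 11.9% | 5.1% |
| 0.5 | 0.3 | 1.30 | 21.5% | 4.8% |
| 0.5 | 0.5 | 0.97 | 16.9% | 5.1% |
| 0.5 | 0.7 | 0.63 | 13.0% | 5.6% |

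Second setting: means 3, 2, 2; SDs 1.3, 1.7, 1.3; component correlation 0 to 0.4; retest correlation 0.3 to 0.7; only trials with 3 to 8 patients at or above 7. ANOVA on change rejects in about 9 to 20% of trials, ANOVA on the follow-up score in about 6 to 25%, and ANCOVA in about 5%. The two ANOVAs fail in opposite conditions: change is worse when retest correlation is low, follow-up score when it is high.

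**4. Endoscopic split, first setting, ANOVA on change.** 3.9 to 4.3% at component correlation 0, 5.0 to 5.9% at 0.3, and 5.7 to 8.2% at 0.5.

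**5. How often the PDAI split can be analysed.** With the second setting's SDs, an assumed mean total of 7 leaves 3 to 8 patients at or above the cut in 89 to 92% of trials. An assumed mean total of 9.5 does so in only 12 to 34%. Where the split does occur, the bias on change remains (12 to 21%).

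**6. What a null result can show.** By the noncentral t at two-sided 5%, 80% power needs a difference of 1.91 SD at 5 versus 6 patients and 2.13 SD at 3 versus 8. Power for a true 1 SD difference is about 32% and 26%.

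**The case against.** The strongest reply is that the ANOVA may never be applied this way. Section 9 gives PDAI and QOL scores their own before-and-after tests, and the objective that mentions an endoscopic split concerns the microbial environment. A natural reading is ANOVA on microbiome data or on baseline characteristics, where this argument does not arise. The primary endpoint in section 10 is resolution without relapse, not a mean score. This stands, and it is why the point is conditional. It does not remove the point, because section 9 does not exclude the clinical score and names no covariate.

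The simulation is also most telling when patients straddle the cut. Section 6 plans patients with pouchitis, so most may score 7 or more. That stands too, although section 3.7 admits patients without pouchitis.

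Several stronger readings are tempting but not supported:

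- **Three splits, each tested at full alpha.** No alpha is stated. Section 3.7 sets out one explicit pair of categories, PDAI of at least 7 is a diagnostic definition, and antibiotic class is only recorded. Three independent 5% tests would give 1 − 0.95³ = 14.3%, but no text says that all three will be run.
- **A chance finding is likely.** A figure above one half requires many inferred splits, outcomes and visits to be tested together.
- **The grouping is the clinical score itself.** It is the total PDAI, of which clinical points are one third.
- **The ANOVA steers future enrolment.** Section 9 gives that decision to a Simon two-stage design.

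**Conclusion.** The point holds in a conditional form and is minor. If the clinical mPDAI after FMT, or its change, is compared by plain ANOVA across total PDAI of at least 7 versus below 7, the false-positive rate is roughly 9 to 21% on change and 6 to 25% on the follow-up score, against about 5% with baseline adjustment.

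These figures rest on an assumed 5% test, assumed component means and SDs, component correlation of about 0 to 0.4 (0.5 in one set of runs) and retest correlation of 0.3 to 0.7. The result for ANCOVA also assumes that endoscopy and histology relate to the later clinical score only through the baseline clinical score. QOL was not simulated; adjusting it for its own baseline follows the same principle. Pilot status explains the absence of a power calculation, but it does not make plain ANOVA the better choice here.

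**What to change.** Add to section 9:

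1. Any between-group comparison of clinical mPDAI or QOL after FMT will use ANCOVA adjusted for the pre-FMT value of the same score. For the clinical mPDAI, use the enrollment value, since that is the one entering the total PDAI.
2. Results will be given as a difference with a 95% CI and treated as exploratory. A non-significant result will not be read as no difference.
3. The comparison is between the two patient categories in section 3.7.

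Section 3.7 should also be reconciled with itself. It describes symptomatic patients without endoscopic and histologic evidence and with PDAI below 7 as not having pouchitis. They fit neither category, because both categories require histologic evidence.

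The cost is a few sentences and one degree of freedom (error df falls from 11 − 2 = 9 to 11 − 3 = 8). No new data are needed, since pre-FMT mPDAI and QOL are already collected. The sponsor gives up significance claims for subgroups. Adjustment removes the artefact but does not make a comparison within 11 patients informative.

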10. ENDPOINTS

The primary endpoint of this study will be resolution of clinical pouchitis symptoms using the clinical component of the modified pouchitis disease activity index without relapse for 3 months. Secondary endpoints include 16S ribosomal gene sequencing and metabolomic profiles that are more favorable (as defined by the donor microbiota). An additional secondary endpoint will be improvement of quality of life as determined by QOL questionnaires.

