1. SPECIFIC AIMS

The aims of this study are: 1) to determine the utility of fecal microbiota transplantation (FMT) in the treatment of patients with ulcerative colitis (UC) associated chronic antibiotic-dependent pouchitis (CADP) and chronic antibiotic refractory pouchitis (CARP) and 2) to study the changes in the microbial environment in patients with pouchitis (pre- and post-treatment) and 3) to assess the impact of therapy on the patient's perceived quality of life.

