2. BACKGROUND AND RATIONALE

The spectrum of inflammatory bowel diseases (IBO) includes ulcerative colitis (UC) and Crohn's disease (CD). The etiology of these diseases is not clear but appears to involve aberrant immunological responses to intestinal bacteria in a genetically predisposed host. There is increasing evidence that the intestinal microbiota play an important role in the initiation and maintenance of IBO. Studies have demonstrated that the microbiota in patients with IBO differ from the healthy non-IBD individuals with a decrease in species such as *Clostridium leptum* and *Faecalibacterium prausnitzii*. This "dysbiosis" may result in fewer bacteria that produce short chain fatty acids which are important in protecting intestinal epithelium. The intestinal microbiota is important in maintaining homeostasis in the intestine and interacts with the host immune system to enhance immune function. Manipulation of the gut bacteria through the use of antibiotics, probiotics, and prebiotics have been shown to be beneficial in IBO. The use of antibiotics for the treatment of mild to moderate active FMT in UC-associated Pouchitis

Version 3.0, date finalized 06/26/2017

colonic Crohn's disease is effective in many cases. Antibiotics are often used to treat acute episodes of UC-associated pouchitis, an inflammatory condition seen in patients who undergo a restorative proctocolectomy with an ileal pouch anastomosis (IPAA). Probiotics (such as VSL-3) for the treatment of acute UC-associated pouchitis as well as for the secondary prevention of repeated episodes of pouchitis have been evaluated in several studies with positive results.

Greater than 50% of IBO patients who undergo an IPAA will develop pouchitis. Many of these patients will develop recurrent episodes of pouchitis and up to 5% will develop chronic pouchitis requiring maintenance therapy with antibiotics or other agents and may even pouch excision. The etiology of pouchitis is unknown, but theories include fecal stasis leading to bacterial overgrowth and alteration of normal commensal flora in a genetically susceptible individual. Microbiome studies in UC pouch patients have shown alterations in the fecal flora with increases in anaerobic bacteria and sulfate producing bacteria.

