All activities outlined in **Table 1** would be billed to the sponsor to compensate [name] for her time and effort to support our participants and overall project goals and needs. The donor related activities will take place before the research participant is seen for informed consent during the screening visit (see **Table 2**). This is done to ensure that the donor has been screened for infectious diseases in a timely manner and that [name] has ample time to prepare the allogenic human fecal specimen in her lab for the transplant on the enrollment visit. Donors will be screened every four weeks which is standard protocol for [name] lab. More details about the donor screening process and requirements are listed in the protocol section **3.6 a) Donor Stool Collection and Processing**.

Table 1. Donor Related Study Activities

Donor Activity	Specific Test Ordered	Visit
Blood/Serology Testing	
 1. Hepatitis A IgM and IgG 2. Hepatitis B S Ab/Sag/Core Ab 3. Hepatitis C Ab 4. RPR 5. Human Immunodeficiency Virus (HIV) 1 and 2 Antibody 	Donor Screening (every four weeks)
Stool Testing	
 1. Clostridium Difficile PCR 2. Salmonella, Shigella, and Campylobacter 3. Ova and parasites 4. H. Pylori antigen 5. 5.Vancomycin resistant Enterococcus (VRE) 6. Carbapenemase resistant Enterobacteriaceae 	
Fecal Sample Preparation for Donation ¹	N/A	

¹The fecal sample will be prepared for the FMT in [name] laboratory on site. Please refer to section 3.6 a for more detailed information regarding the donor fecal sample processing activities.

Table 2 outlines a total of five complete research visits for each research participant: screening (initial), enrollment (transplant), 2 weeks post-transplant (may be a phone call at the discretion of the physician), 4 weeks post-transplant, and 3 months post-transplant. For the initial or screening visit, research participants will first complete the informed consent process with a member of the research team. Upon completion of the informed consent process, the participant will receive phlebotomy to collect blood for plasma chemistries, CBC with differential, and platelet counts.

Urine will also be collected and screened for basic urinalysis. Women of child bearing potential

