(WOCBP) will be screened using urine pregnancy kits to test for beta HCG levels. These kits will be provided by the sponsor. The results of these kits will be used as the final determination of pregnancy for WOCBP. WOCBP who screen positive for beta HCG (i.e. are pregnant) will be excluded from the study for the safety of both the mother and her unborn child. Phlebotomy for plasma collection, eventual CBC with differential, and platelet count will be performed for each research visit. Urine and stool will also be collected for each study visit. In addition to phlebotomy, urine collection, and stool collection, research participants will also receive a physical exam for each research visit.

Waist and hip circumference will be measured during the screening visit only. For the second visit (i.e. enrollment), the research participant will also receive a physical exam along with a flexible sigmoidoscopy. The flex sigmoidoscopy will be performed under moderate sedation using propofol per usual anesthesia services. The flexible sigmoidoscopy will be used to gain access to the pouch and to take a mucosal tissue pouch biopsy.

Table 2. Research Participant Study Activities

Visit Procedures	Screening²	Enrollment	2 Week³ (+/- 3 days)	4 weeks (+/- 7 days)	3months (+/- 14 days)
Informed Consent Process	X				
Physical Exam	X	X	X	X	X
Urine pregnancy testing for WOCBP	X				
Phlebotomy	X	X	X	X	X
Labs and Specimen Processing:					
Stool collection	X	X	X	X	X
Plasma collection	X	X	X	X	X
Urine collection	X	X	X	X	X
CBC w/diff., platelet count ⁴	X	X	X	X	X
Flexible Sigmoidoscopy with Moderate Sedation		X			
Mucosal Biopsy Collection		X			
Waist and hip circumference measures	X				
Fecal Microbiota Transplant		X			

Modified PDAI	X (clinical)	X	X (clinical)	X(clinical)	X (clinical)
Quality of Life Questionnaires	X			X	X
Food Recall Questionnaire		X		X	X

²If both screening and enrollment visits occur within 7 days, research samples may not be recollected at the enrollment visit, at the discretion of the investigator

³The 2-week visit may be conducted over the telephone for subjects who live a significant distance from the study site and at the discretion of the study investigator. Biological samples will not be collected on subjects who complete visit via telephone, however subject may be asked to mail in a stool sample for testing

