- Biohazard containers for disposal of contaminated materials are readily accessible in the processing area.
- Good laboratory techniques will be exercised to minimize the formation of aerosols, droplets, spatters, splashes.

The FMT processing (performed by [name]) involves taking of the standard donor's stool which is received in the clinical microbiology laboratory along with a short questionnaire (see Appendix 2). The hood is terminally cleaned with 10% sodium hypochlorite followed by 70% ethanol. The hood area is then lined with clean lab mats. Thirty cubic centimeter (ccs) saline aliquots are poured into 50 ml centrifuge tubes and 1 cm³ of stool is distributed in these aliquot containers. The stool is mixed gently using a tongue depressor until a smooth suspension is formed. The contents are then filtered using a standard Parapak filter. The suspension is allowed to settle in the 50-ml centrifuge tube for 10 minutes and then poured off into a sterile container. This filtrate is then drawn up in 60 cc syringes, and labeled "For Enteral Use Only". Syringes are placed into sealed biohazard labeled bags for transport.

3.6. b) Fecal Microbiota Transplant (FMT) Procedure

Subjects will be asked to clean out their pouch using two over the counter enemas no longer than 3 hours before the procedure time. This is standard of care for patients undergoing routine flexible sigmoidoscopy. Subjects will also be asked to take 4 mg of loperamide (over-the-counter anti-diarrheal medication) one half hour before the FMT.

Subjects will be placed in the left lateral decubitus position with elevated hips in a designated private room in clinic or endoscopy suite for 90 minutes of FMT intervention. Subjects will be asked to rotate 180 degrees slowly during a 10-minute period. Subjects will be monitored for 30 minutes after FMT for any adverse events and discharged.

Concomitant Medications: Permitted concomitant medications: Patients may remain on chronic medications during the study period.

Prohibited medications: Patients will need to be off antibiotics and probiotics for at least 48 hours prior to fecal transplant.

End of the study: The end of study for each patient is defined as the date of the last visit (i.e. 3 month visit post-transplant).

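### The primary endpoint leaves relapse undefined and ignores antibiotics used after FMT, so an antibiotic-dependent subject who is symptom-free on resumed antibiotics can count as a responder

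*Combined protocol and SAP*

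**What the plan says.** Section 10 gives the primary endpoint in one sentence: "resolution of clinical pouchitis symptoms using the clinical component of the modified pouchitis disease activity index without relapse for 3 months". Section 9 adds no rule for resolution, relapse or antibiotics used during follow-up.

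Section 1 names antibiotic-dependent and antibiotic-refractory chronic pouchitis as the conditions under study. Section 2 describes "chronic pouchitis requiring maintenance therapy with antibiotics or other agents". Section 8 presents avoidance of repeated antibiotic courses as the potential benefit.

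On medication, Section 3.6 b has two statements. Under the permitted heading: "Patients may remain on chronic medications during the study period". Under the prohibited heading: "Patients will need to be off antibiotics and probiotics for at least 48 hours prior to fecal transplant". Neither says what applies to antibiotics after the transplant.

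The last two visits are "4 weeks post-transplant, and 3 months post-transplant", with windows of 7 and 14 days either side. Table 2 schedules only the clinical part of the index at the visits after FMT, and it has no medication row. Section 3.7 records earlier antibiotic use and treatments as history, and Section 5 takes prescribed medicines from the chart. Section 12 counts worsening of a pre-existing condition as an adverse event, then limits collection to events related to study procedures.

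**The concern.** Patients with antibiotic-dependent disease are expected to do well on antibiotics. An endpoint that looks only at symptoms cannot tell a subject who is well because of FMT from one who is well because antibiotics were restarted. The second outcome is the one that Section 8 hopes FMT will prevent, yet the wording of Section 10 lets it count as success.

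The data to put this right later are not planned. If antibiotic use after FMT is not recorded with dates as it happens, the only recourse is the chart. Section 3.6 b expects many subjects to travel to the site, so prescriptions written elsewhere may be missing from it. The PDAI and quality-of-life change tests in Section 9 do not use the responder definition, but they too are hard to read without knowing who was on antibiotics when scored.

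**Working it through.** The plan gives no derivation for its 11 subjects and no responder-rate calculation, so there is no figure to reproduce. The check is mainly a reading of the passages together.

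**1. Is resolution or relapse defined anywhere?** The clinical items in Appendix 1 are stool frequency (0-2), bleeding (0-1), urgency or cramps (0-2) and fever (0-1). The maximum is 2 + 1 + 2 + 1 = 6, and no cut-off is given. The only cut-off in the documents is a total PDAI of seven or more (Section 3.7). The clinical component cannot reach it (6 < 7). It also needs endoscopy and histology, which Table 2 schedules only at enrollment, so it cannot serve as a relapse rule during follow-up.

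**2. What applies to antibiotics after FMT?** Before FMT there is a restriction for at least 48 hours. After FMT no restriction, permission or endpoint rule is stated. A subject symptom-free on resumed antibiotics meets the wording of Section 10.

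**3. Would the use be seen?**

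| Source | What it captures | Limit |
|---|---|---|
| Table 2 | No medication row | No scheduled, dated record specified |
| Section 3.7 | Earlier antibiotic use and treatments | History only |
| Section 5 | Prescribed medicines from the chart | No time window, no link to the endpoint |
| Section 12 | Worsening is an adverse event by definition | Collection limited to procedure-related events |
| Appendix 4 | Symptoms over the last 2 weeks | No question on treatment |

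**4. How long could a flare go unscored?** Three months is taken as week 12, the timing that Sections 3.7 and 5 give for the last questionnaires. Week 4 is day 28 (± 7) and week 12 is day 84 (± 14).
- Nominal gap: 84 − 28 = 56 days
- Shortest: (84 − 14) − (28 + 7) = 70 − 35 = 35 days
- Longest: (84 + 14) − (28 − 7) = 98 − 21 = 77 days

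**5. Two routes to a wrongly counted responder.** (a) Maintenance antibiotics are resumed after FMT without a flare, so nothing resembling relapse occurs. (b) A flare occurs between week 4 and month 3, is treated, and has settled by the month 3 score.

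**6. Size.** One subject in 11 is 1/11 = 9.1 percentage points. The documents do not say how many subjects would be affected. As a purely assumed illustration, suppose there are 2 true responders (exact 95% confidence intervals in brackets):
- None wrongly counted: 2/11 = 18.2% (2.3 to 51.8)
- One wrongly counted: 3/11 = 27.3% (6.0 to 61.0)
- Two wrongly counted: 4/11 = 36.4% (10.9 to 69.2)

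**The case against.** **The record may exist.** Table 2 is not exhaustive: it also has no row for adverse events or demographics, which other sections require. Section 5 does collect prescribed medicines, and Section 9 mentions a data abstraction sheet whose contents are not in the documents. A reader might infer that no medication data would exist at all; that goes too far. What stands is that no scheduled, dated record after FMT is specified and none feeds the endpoint.

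**Antibiotics are not clearly permitted.** A reader might infer that the protocol allows maintenance antibiotics to be resumed as chronic medication. That is only one reading. Antibiotics appear under the prohibited heading, and a subject who stopped them for FMT is not obviously remaining on them. The point needs only the silence after FMT.

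**A flare is a relapse in ordinary usage, and a worsening is an adverse event.** Both are true. Section 12 also provides remote and unrelated categories, which fit poorly with collecting related events only, so that section is inconsistent with itself. A flare may therefore be recorded, but the plan does not ensure it. Route (a) involves no flare.

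**This is a small, uncontrolled Phase 1 study.** Its primary objective in Section 3.1 is safety and tolerability, which this point does not touch. Without a control arm, a response rate could not be firmly attributed to FMT even after the fix, and with 11 subjects the interval is wide anyway. These facts limit the consequence. Section 10 still names this the primary endpoint, and the error runs in one direction, which a confidence interval does not reflect.

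**Counting antibiotic use as non-response is one choice of estimand.** It is, but Section 8 points to it. Section 8 does not support extending the rule to probiotics or immunosuppressants.

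**Conclusion.** The point holds and should be fixed. As written, the primary endpoint can count as a responder an antibiotic-dependent subject who is well on resumed antibiotics, and the plan does not secure the data needed to identify that subject. It applies mainly to the antibiotic-dependent part of the population and less to the refractory part.

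The firm figures are 9.1 percentage points per affected subject and a stretch of 56 days (35 to 77 with the windows) without a scheduled score. The day count assumes that 3 months means week 12. The number of subjects affected is unknown, so no overall inflation is claimed. A reader might infer that a wrong decision on further enrolment would follow; the documents do not support this, because Section 9 names a Simon two-stage design but gives no boundaries.

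Whether the entry criteria admit patients without pouchitis (Sections 3.7, 4 and 6 differ) is a separate matter to reconcile, and this point does not depend on it.

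**What to change.** Make three changes, for analysis and data collection only, without restricting care:

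1. In Section 10, count antibiotics started or resumed for pouchitis between FMT and month 3 as non-response. List courses given for unrelated indications separately.
2. In Table 2, add a record of antibiotics and other pouchitis medication (drug, indication, start and stop dates) at every visit after FMT, including a 2-week visit held by telephone. At month 3, also ask about any flare since week 4.
3. State in advance which clinical sub-score (0-6) counts as resolution and what change from it counts as relapse.

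The permitted and prohibited medication statements in Section 3.6 b should also be reconciled so that they say what applies after FMT. What they should say is for the investigators to settle.

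The cost is protocol wording, one data field per visit and one question at month 3, with no extra visit or sample. The responder rate may look less favourable.
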